2.1 Primary Endpoints

2.1.1 Evaluate the change in level of self-reported financial burden from baseline (within 60 days of diagnosis) to 12 months after diagnosis of colon or rectal cancer treated with curative-intent.

2.2 Secondary Endpoints

- 2.2.1 Evaluate reported access and utilization of financial services (i.e. financial counselor, navigator, social workers) and its association to financial burden in the first 12 months after diagnosis of colon or rectal cancer treated with curative-intent.
- 2.2.2 Evaluate the change in level of self-reported financial burden and employment limitations from baseline (within 60 days of diagnosis) to 3, 6, and 12 months after diagnosis of colon or rectal cancer treated with curative-intent.
- 2.2.3 Evaluate long term outcomes at 24 months after diagnosis including financial burden, employment limitations and adherence to clinical follow-up guidelines.
- 2.2.4 Evaluate the change of quality-of-life outcome (QoL) from baseline to 12 months and its association with predictors.
- 2.2.5 Evaluate the change in level of self-reported financial burden from baseline to 12 months using alternate measures of financial burden (i.e. impact of cost questions and single item from EORTC Q30)

3. Selection of Sites

All interested NCORP sites will be invited to participate. There will be no specific exclusion criteria (i.e. minimum number of cases) because we would like to include a wide variety of different systems to better understand the variability in available financial resources and patient experiences. To ensure patient diversity in this study, all Minority/Underserved National Cancer Institute Community Oncology Research Programs (MU NCORP) sites will be specifically invited to participate.

4. Selection of Patients

Each of the criteria in the checklist that follows must be met in order for a patient to be considered eligible for this study. Use the checklist to confirm a patient's eligibility. For each patient, this checklist must be photocopied, completed and maintained in the patient's chart.

In calculating days of tests and measurements, the day a test or measurement is done is considered Day 0. Therefore, if a test is done on a Monday, the Monday four weeks later would be considered Day 28.

ECOG-ACRIN Patient No. _____

Patient's Initials (L, F, M)

NOTE: CTEP Policy does not allow for the issuance of waivers to any protocol specified criteria

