7.1.7 Study Measures and Objectives Table

Patient Questionnaires	Objectives
Baseline Questionnaire	Sociodemographics, comorbities, insurance information. Used as predictor variables for all objectives
Sociodemographic Follow-up	Sociodemographics and insurance information. Used as predictor variables for all objectives
Baseline Employment	Secondary Endpoint (2.2.2)
Follow-up Employment	Secondary Endpoint (2.2.2). Employment asked at baseline, 6, 12, and 24 months as these are time points in cancer continuum that we hypothesize change and we want to understand longitudinal change. We omitted 3 month due to patient burden. We include a 24 month time point to understand long term survivorship employment limitations.
FACT-G7	Secondary Endpoint (2.2.4). QOL asked at baseline, 6, 12, and 24 months as these are time points in cancer continuum that we hypothesize change. We omitted 3 month due to patient burden. We include a 24 month time point to understand long term survivorship QOL
Self-Efficacy	This will be used as predictor variable for all objectives. To limit burden we omitted 3 and 12 month
COST	Primary Endpoint (2.1.1)- needed at all time points to understand changes at diagnosis (baseline), beginning of tx (3), end of therapy (6), short term survivorship(12), and long term survivorship(24).
Impact of Cost	Secondary Endpoint (2.2.5)- needed at all time points to understand changes at diagnosis (baseline), beginning of tx (3), end of therapy (6), short term survivorship(12), and long term survivorship(24).
Access and Utilization of Financial Resources	Secondary Endpoint (2.2.1)- needed at all time points to understand changes at diagnosis (baseline), beginning of tx (3), end of therapy (6), short term survivorship(12), and long term survivorship(24).
Acceptability	Because of sensitive nature of questions will include these questions to assess acceptability at the 12 month time point.
Site Completed Forms	
Site Survey	Assesses available resources for financial assistance. Will be used as predictor variable
Baseline Clinical Form	Clinical information collected at all time points to correlate with primary endpoint of financial burden
Follow-up Clinical Form	Clinical information collected at all time points to correlate with primary endpoint of financial burden
24-month Follow-up Clinical Form	Clinical information and adherence variables collected for Secondary Endpoint (2.2.3)

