11.4 Statistical Analysis Plan

11.4.1 Primary Objective

The primary aim is to evaluate the change in the level of self-reported financial burden from baseline (within 60 days of diagnosis) to 12 months after diagnosis of colon or rectal cancer treated with curative-intent.

We will calculate the difference of COST measurements from baseline to 12-month FU for the completers who provide data at both time points, and use the paired t-test to assess if the mean difference is significantly different from zero. In case the data are not normally distributed, nonparametric methods (e.g., Wilcoxon signed-rank test) will be used instead to assess the difference. For the participants with missing measurements at one time point, we will implement the methods as described in Section 11.4.3 to handle the missing values. The two results will be compared as a sensitivity analysis.

In addition, linear regression models with the change of COST from baseline to 12-month FU as the response variable will be fit to investigate the impact of other factors, including demographics variables (e.g., age, sex, marital status), clinical variables (e.g., stage of disease, malignancy type, chemotherapy status), baseline questionnaire variables (e.g., self-efficacy,). The three-level treatment status (IV chemotherapy, chemotherapy without IV, and no chemotherapy) will also be evaluated as a predictor. The impact of system level variables (including being designated a minority/underserved site or not, availability of financial resources for patients) will be examined in the regressions as well. Since pregnant women may have higher health-care related costs, the response will be compared between pregnant women and the others; if significant, the subset analysis may be performed in this population.

- 11.4.2 Secondary Objectives
 - 11.4.2.1 Evaluate reported access and utilization of financial services (i.e. financial counselor, navigator, social workers) and its association to financial burden in the first 12 months after diagnosis of colon or rectal cancer treated with curative-intent.

The 8-question CCVI measure as described in Section 7.1.2 will be analyzed to evaluate the change from

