To evaluate the change of financial burden from baseline to the other time points (i.e., 3-month, 6-month, and 24month), the similar approaches described for the primary objective's assessment will be implemented. In addition, longitudinal data analysis will be conducted to estimate the measurements' trajectory across all five times points. Specially, linear (or generalized linear) mixed model will be fit to study the change in the mean response over time and also the effects of cancer type, stage, treatment plan and demographics, etc. on financial burden. In case the changes in the mean response over time are not linear, the quadratic trends or non-linear trends via spline may be considered in the modeling (61). Interactions will be evaluated as well. The above analyses may be repeated to explore the categorized COST measures (63, 64).

Logistic regressions will be fit to study whether or not the level of financial burden will impact the patient's adherence to clinical follow-up guidelines, which is defined as follows: "adherent" is defined as completing all of the follow up guidelines within the 24 month study period and includes an endoscopic evaluation of their colon or barium enema, routine history and physical at least twice, and serum carcinoembryonic (CEA) level checked at least twice. The details of adherence questions can be found in Section 9.2.4.1.

11.4.2.4 Evaluate the change of quality-of-life outcome (QoL) from baseline to 12 months and its association with predictors

FACT-G7, as described in Section 7.1.4, will be analyzed to evaluate the change of QoL from baseline to 12 months. The sum of the 7-item scores will be modeled as a continuous variable in the linear regressions (57). The predictors will include demographics (age, sex, marital status), clinical variables (stage of disease, malignancy type, chemotherapy status), and financial variables (COST score). Similar to the primary aim assessment, the impact of the baseline questionnaire variables (e.g., self-efficacy) and the system level variables (including being designated a minority/underserved site or not, availability of financial resources for patients) will be examined in the models as well. FACT-G7 at 6 months will be included as an adjustment covariate. Similar analysis will be conducted to evaluate the change of FACT-G7 from baseline to 24 months as well.

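### The model for predictors of 12-month FACT-G7 change adjusts for 6-month FACT-G7, so its coefficients are conditional on a post-baseline value of the outcome, and no model without it is planned

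*Combined protocol and SAP*

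**What the plan says.** Secondary endpoint 2.2.4 reads "Evaluate the change of quality-of-life outcome (QoL) from baseline to 12 months and its association with predictors". Section 11.4.2.4 implements it: FACT-G7 "will be analyzed to evaluate the change of QoL from baseline to 12 months", and "The sum of the 7-item scores will be modeled as a continuous variable in the linear regressions". The predictors are demographic and clinical variables (among them stage, tumour type and chemotherapy), the COST score, baseline questionnaire variables such as self-efficacy, and site-level variables. The paragraph then states, without condition or reason, "FACT-G7 at 6 months will be included as an adjustment covariate". Baseline FACT-G7 is not listed as a covariate, and the visit of the COST score is not given.

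For the later time point the section adds "Similar analysis will be conducted to evaluate the change of FACT-G7 from baseline to 24 months as well", without saying whether the 6-month covariate carries over.

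On timing, Section 7.1.7 says "QOL asked at baseline, 6, 12, and 24 months as these are time points in cancer continuum that we hypothesize change".

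Two analyses of COST handle the same situation differently. In Section 11.4.1, "linear regression models with the change of COST from baseline to 12-month FU as the response variable will be fit", and no interim COST value is named as a covariate. In Section 11.4.2.3, repeated COST scores are outcomes: a "linear (or generalized linear) mixed model will be fit to study the change in the mean response over time".

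**The concern.** The 6-month FACT-G7 score falls inside the 0-to-12-month interval whose change is being explained. Section 7.1.7 expects quality of life to change at that visit. Section 1.2.6 places most patients near the end of treatment at 6 months and finished by 12, so chemotherapy, for example, could plausibly act differently at the two visits. A predictor that has already moved the 6-month score has part of its relation to the outcome passed through the covariate.

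The coefficient then answers a narrower question: among patients with the same 6-month score, how does 12-month change differ by predictor? Endpoint 2.2.4 asks for the association with 12-month change itself. A reader of the results would naturally take the coefficients in that overall sense, and nothing else in the plan supplies it. The mixed model in 11.4.2.3 concerns financial burden. The sensitivity analyses in 11.4.2.5 and 11.4.3 concern other burden measures and missing data.

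**Working it through.** **No figure to reproduce.** The documents state no effect size, power or correlation for FACT-G7. The correlations of 0.2 and 0.4 in Section 11.3.2 are for COST between baseline and 12 months and do not apply here.

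**Assumptions.** Scores have unit SD. A predictor has no association with baseline FACT-G7 and shifts the 6-month score by d6 and the 12-month score by d12. The correlations are r(0,6), r(6,12) and r(0,12). The response is the change from baseline to 12 months, and 6-month FACT-G7 is the only FACT-G7 covariate, as the text lists.

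**Formula.** Within predictor groups, the slope of change on the 6-month score is k = r(6,12) - r(0,6). The fitted predictor coefficient is therefore d12 - k × d6. Without the covariate it is d12.

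**Range.** With both correlations between 0.4 and 0.7, either can be the larger, and k runs from 0.4 - 0.7 = -0.3 to 0.7 - 0.4 = +0.3.
- Equal effect at both visits (d6 = d12): retained share 1 - k, from 70% to 130%.
- A 0.5 SD drop at 6 months only (d6 = -0.5, d12 = 0): coefficient 0.5 × k, from -0.15 to +0.15 SD, where the overall value is 0.
- Equal correlations: k = 0 and there is no shift. This is possible, since both intervals are 6 months.
- In steps of 0.05 there are 7 × 7 = 49 correlation pairs. Of these, 7 + 12 + 10 = 29 (59%) have |k| of 0.10 or less, which shifts the coefficient by at most 0.10 × 0.5 = 0.05 SD for a 0.5 SD 6-month effect.

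**Simulation check** (400,000 patients, binary predictor, effect -0.5, r(0,12) = 0.4):

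| r(0,6) | r(6,12) | Equal effects: formula / simulated | 6-month only: formula / simulated |
|---|---|---|---|
| 0.4 | 0.7 | -0.35 / -0.352 | +0.15 / +0.148 |
| 0.5 | 0.5 | -0.50 / -0.507 | 0.00 / -0.007 |
| 0.7 | 0.4 | -0.65 / -0.650 | -0.15 / -0.150 |

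The same data without the 6-month score give -0.50 and 0.00, within 0.006.

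**Other readings of the paragraph.**
- If the response is the 12-month sum, the coefficient is d12 - r(6,12) × d6. The retained share is 1 - r(6,12), or 30% to 60%.
- If baseline FACT-G7 is also in the model, the retained share is 1 - [r(6,12) - r(0,12) × r(0,6)] / [1 - r(0,6)²]. With r(0,12) between 0.3 and 0.5 it runs from 1 - (0.7 - 0.21)/0.51 = 4% to 1 - (0.4 - 0.35)/0.51 = 90%.

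**Precision given up.** The 6-month score explains k² / (2 - 2 × r(0,12)) of the variance of change. With r(0,12) between 0.3 and 0.5 this is at most 0.09 / 1.0 = 9%. Dropping it widens the standard error by at most 1/√(1 - 0.09) - 1 = 4.8%.

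**The case against.** A conditional association is still an association, so the planned model is a permissible answer to the second half of endpoint 2.2.4. The shift may be small or nil: over most of the assumed range it is at most 0.05 SD for a 0.5 SD 6-month effect. The COST analyses concern another outcome, so their different handling does not show that this one is an error. All of this stands, and it limits the size of the point. It does not remove it. The plan gives no reason for the conditional version, speaks of the impact of some of these variables, and provides no overall version beside it. The documents contain nothing from which to conclude that the two correlations are equal.

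The COST coefficient is a possible exception. If the 12-month COST score is meant, 6-month quality of life precedes it and could be a legitimate confounder. This also stands, for that one coefficient.

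A reader might go further and infer that the coefficients are necessarily wrong, or always pulled toward zero. The documents do not support this. With change as the response, the coefficient equals the overall association when the two correlations are equal, and it is exaggerated rather than weakened when r(0,6) exceeds r(6,12) and the effects at the two visits are equal. A reader might also take the severe losses under the other two readings as the expected result. Those need a 12-month sum as response or a baseline FACT-G7 covariate. The section describes an analysis of change, so the reference to the sum of items may be no more than a scoring description, and it lists no baseline covariate.

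**Conclusion.** The structural point holds with high confidence. The QoL predictor model conditions on a post-baseline value of its own outcome, and no model without that value is planned. The consequence is less certain. Neither the size nor the direction of the shift follows from the documents. Under the stated assumptions (unit SDs, no baseline association, both correlations 0.4 to 0.7, change as response) the model retains 70% to 130% of an equal effect, and a 0.5 SD effect seen only at 6 months appears as -0.15 to +0.15 SD at 12 months, with zero possible.

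The point is confined to the association half of one secondary endpoint and to the 24-month analysis modelled on it. It does not reach the primary COST test, the mean FACT-G7 change or the sample size. It should be fixed because the remedy is cheap and the overall association is what the endpoint names.

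**What to change.** In Section 11.4.2.4:
- Make the main 12-month association model one without 6-month FACT-G7, and state that the response is the change from baseline.
- State that the 24-month model also omits it.
- If the 6-month score is still of interest, keep a model that includes it as a labelled conditional or exploratory analysis, or treat the score as a repeated outcome in a mixed model, as Section 11.4.2.3 already does for COST.

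Two clarifications are separate and optional: whether to adjust for baseline FACT-G7, and which visit's COST score is the predictor. The second would settle whether a 6-month-adjusted model is justified for the COST coefficient.

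The cost is two or three sentences in the SAP, and all the data are already collected. The downside is the loss of any precision that the 6-month score brings, at most a 4.8% wider standard error on the assumed correlations.

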11.4.3 Handling Missing Data

As stated in the Section 11.3.3, we will closely monitor the patient attrition and determine whether the dropout is informative or not. If the missing is random, we may implement the method like multiple imputation to impute the missing values. In case the missing is not random (e.g., patients who are lost to follow up may experience more financial burden), we will implement various methods for the adjustment in our analysis, e.g., Bayesian modeling with informative priors. Analysis under different scenarios will be conducted to explore sensitivity to different missing data assumptions (65).

Since the COST is an 11-item PRO measure of financial toxicity, it is likely that partial data might be collected from some patients. According to the FACIT guidelines (www.facit.org), the patients who answer less than 6 out of 11 items will be excluded from the analysis. For patients who answer more than 6 but less than 11 items, the normalized score will be recorded according to the following formulae:

(sum of individual item scores)* 11 / the number of items answered.

12. Electronic Data Capture

Please refer to the EAQ162CDForms Completion Guidelines for the forms submission schedule. Data collection will be performed in Medidata Rave and EASEE-PRO.

This study will be monitored by the Clinical Data Update System (CDUS) version 3.0. Cumulative CDUS data will be submitted quarterly from the ECOG-ACRIN Operations Office – Boston to CTEP by electronic means.

13. Patient Consent and Peer Judgment

Current FDA, NCI, state, federal and institutional regulations concerning informed consent will be followed.

14. References

- 3. De Souza JA. The cost of cancer care: there is more than one elephant in the room. Oncology. 2012; 26: 926-8.

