11.3.2 Sample Size

Based on the data from previous cross-sectional studies (42, 50), we assume that the baseline COST score follows a normal distribution with the mean 25 and the standard deviation 12 and the 12-month FU score follows a normal distribution with the mean 22.5 and the standard deviation 12. Thus, the effect size of change is assumed to be 10%. The correlation between the baseline and the 12-month FU scores is assumed to be 0.2. Based on these assumptions, a sample size of 394 cancer patients will be needed to achieve a 90% power to detect the 2.5 difference (i.e., 10% change) at the 0.05 significance level using a two-sided Wilcoxon Signed-rank Test. These results are based on 20,000 Monte Carlo samples for the sample distributions under the null and the alternative hypothesis. The sample size will be 296 if the power remains at 0.90 and the correlation is assumed to be 0.4. A pilot study assessing financial burden among patients with advanced cancers had a 24% attrition rate between baseline and 12 month assessments, excluding those who died before the 12 month time point (36). An ongoing study on employment among cancer patients across the stage spectrum had a 30% attrition rate at the 12month follow-up ([name], personal communication). Therefore, we assume a 30% attrition rate at the 12-month follow-up and expect to enroll 563 patients into the study. Note: The imputation was based

on Monte Carlo samples in simulations, which caused slight fluctuations in the sample size. However, with 20,000 simulations, the fluctuation rate is only about 1%.

With these sample sizes, we will have the power of 1.0 to detect a difference of 5 (i.e., 20% change) from the baseline to the 24-month FU score, while the latter is assumed to follow a normal distribution with mean 20 and standard deviation 12. The above computations were done using PASS 14 (83).

Table 4: Power A	nalysis. Power:	0.80 and 0.90.	Correlation:	0.20 and 0.40.
------------------	-----------------	----------------	--------------	----------------

Power 0.797 (0.006) [0.791	N 292 0.802]	H0 Diff0 0.0	H1 Diff1 2.5	Corr R 0.200	Target Alpha 0.050	Actual Alpha 0.050 (0.003) [0.047	Beta 0.203 0.053]
0.803 (0.006) [0.798	218 0.809]	0.0	2.5	0.400	0.050	0.049 (0.003) [0.046	0.197 0.052]
0.900 (0.004) [0.896	394 0.904]	0.0	2.5	0.200	0.050	0.051 (0.003) [0.048	0.100 0.054]
0.904 (0.004) [0.900	296 0.908]	0.0	2.5	0.400	0.050	0.051 (0.003) [0.048	0.096 0.054]

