11.3.3 Accrual and Attrition Monitoring

It is expected that the monthly accrual for this trial will be approximately 15 to 16 cases, excluding the first 6 months as institutions obtain IRB approval. Therefore, we anticipate that 563 participants will be enrolled in about 3 to 3.5 years.

After assessing the preliminary data in [name]'s employment study (still ongoing), we didn't observe an obvious pattern of the dropout that associates with cancer type, stage, or employment status. Thus, we will not implement the adaptive design in our study. However, we will closely monitor the patient's attrition and then determine if the attrition rate will be significantly different among various groups. Accordingly, the protocol may be amended and the sample size may need to be adjusted to oversample patients for the groups with high attrition rates.

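### Section 11.4.3 picks the missing-data method from attrition monitoring, which cannot show whether dropout depends on the unseen 12-month COST score

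*Combined protocol and SAP*

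**What the plan says.** Under Section 11.4.1 the change in COST from baseline to 12 months is tested with a paired t-test, or a Wilcoxon signed-rank test if the data are not normal, "for the completers who provide data at both time points". The text continues: "For the participants with missing measurements at one time point, we will implement the methods as described in Section", where the section meant is 11.4.3. The two results are then compared as a sensitivity analysis.

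Section 11.4.3 opens by referring back to Section 11.3.3 and states that "we will closely monitor the patient attrition and determine whether the dropout is informative or not". In 11.3.3 the monitoring is meant to "determine if the attrition rate will be significantly different among various groups". The consequence named there is a possible amendment to oversample groups with high attrition.

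Section 11.4.3 then splits into two branches:

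- The first is optional in its wording: "If the missing is random, we may implement the method like multiple imputation to impute the missing values".
- The second covers non-random loss and gives an example: "In case the missing is not random (e.g., patients who are lost to follow up may experience more financial burden"). Here unspecified adjustments follow, with Bayesian modelling under informative priors as the example.

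The paragraph closes with a general promise: "Analysis under different scenarios will be conducted to explore sensitivity to different missing data assumptions (65"). No shift, prior, range or estimator is given for those scenarios.

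Neither 11.4.1 nor 11.4.3 mentions death. Section 11.3.2 cites a pilot attrition rate "excluding those who died before the 12 month time point", and the Follow-up Clinical Form (Section 9.2.3) records vital status at 3, 6, 12 and 24 months.

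**The concern.** The choice of method hangs on a finding that the monitoring cannot supply. Data are not missing at random when dropout still depends on the unobserved score after allowing for everything recorded. Counts of who left, by recorded group, carry no information about that.

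The inference fails in both directions. If attrition differs by a recorded group, an imputation model that includes the group can deal with it, so unequal rates are no evidence against missing at random. If attrition is even, patients in every group may still have left because their burden rose, which is the plan's own example of non-random loss.

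At stake is the value of the check. The adjusted analysis is there to test a completer result that is expected to lose 30% of patients. If even attrition leads the team to assume missing at random, both analyses can be wrong in the same direction, and their agreement would be taken as reassurance.

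**Working it through.** **Inputs (Section 11.3.2).** Mean COST 25 at baseline and 22.5 at 12 months; SD 12 at both; correlation 0.2; two-sided 0.05; 90% power; 394 evaluable; 30% attrition; 563 enrolled. Higher COST is better, so the planned change is -2.5.

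**The plan's own figures.** SD of change = 12 × √(2 × (1 - 0.2)) = 15.18. The paired normal formula gives n = (15.18 × (1.960 + 1.282) / 2.5)² = 388, against 394 stated. Simulating the Wilcoxon test at n = 394 (20,000 samples) gives power 0.890. Inflation: 394 / 0.70 = 562.9, so 563. The figures reproduce, and this point does not change the sample size.

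**What the observed data leave open.** Whole-cohort change = completer change + 0.30 × (leaver change - completer change). With a completer change of -2.5:

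| Leavers minus completers (points) | Whole-cohort change |
|---|---|
| -8.33 | -5.0 |
| -5 | -4.0 |
| 0 | -2.5 |
| +5 | -1.0 |
| +8.33 | 0.0 |

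The same completer data and the same attrition table fit every row. Since 2.5 / 0.30 = 8.33, a difference of that size doubles or removes the effect. Equally, if completers showed no change, leavers worse by 8.33 points would put the whole cohort at -2.5.

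**Whether a group comparison would notice.** The simulation used 563 patients, a true change of -2.5, 30% dropout, four equal groups unrelated to COST, and 2,000 runs per row. The log-odds of dropout rise by β for each SD of worse unseen 12-month COST (β is an assumed range). The missing-at-random (MAR) estimate imputes 12-month COST by regression on baseline.

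| β | Group attrition test rejects | Completer mean | MAR estimate | Power of completer t-test |
|---|---|---|---|---|
| 0 | 5.6% | -2.49 | -2.50 | 91% |
| 0.3 | 5.0% | -1.63 | -1.45 | 58% |
| 0.5 | 5.1% | -1.10 | -0.83 | 30% |
| 0.8 | 5.5% | -0.44 | -0.04 | 8% |
| 1.0 | 4.0% | -0.07 | +0.42 | 4% |

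The attrition test rejects at about its false-positive rate throughout. At β = 0.3 the completer and MAR results differ by only 0.18 points (1.63 - 1.45), while they miss the truth by 0.87 and 1.05.

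**Which way a sensitivity shift must run.** The completer standard error is 15.18 / √394 = 0.765. A change of -2.5 loses significance once it shrinks to about 1.96 × 0.765 = 1.50, a shift of +1.00, which needs leavers better by 1.00 / 0.30 = 3.3 points. This is rough, because the standard error after imputation will differ. Lowering imputed scores only moves the estimate further from zero, so a grid in that direction alone cannot overturn the planned decline.

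**The case against.** Four things can fairly be said for the plan.

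- The closing commitment in 11.4.3 to examine different missing-data assumptions is firm and does not depend on how dropout is classified. A reader might infer that a quiet attrition table would let the plan assume away its own named scenario, but that sentence does not allow it. What remains is that the scenarios have no parameters and could be chosen after the data are seen.
- The completer comparison comes first in 11.4.1, and the 11.4.3 result is set beside it. It would be wrong to say that the faulty rule selects the main result. It selects the check on it.
- The link from a non-significant attrition test to a verdict of random missingness is partly inferred. In 11.3.3 the stated use of the comparison is oversampling, and other evidence is collected: reasons for missed questionnaires (6.4.5.3), and performance status and insurance changes (9.2.3). Section 11.4.2.3 also plans a mixed model over all five time points, whichever branch is taken. These data can make missing at random more plausible, but they cannot establish it, and 11.4.3 names no other means of deciding.
- A reader might infer that COST will be imputed for patients who have died. No section says so, and imputation is itself only optional. Nor does the 30% planning rate set deaths apart: the exclusion belongs to the 24% pilot rate, and 30% follows an employment study with no stated exclusion. Deaths should also be fewer than in the pilot, which included advanced disease, because eligibility is stage I-III with life expectancy of at least 24 months. What stands is that the plan is silent on death.

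**Conclusion.** The concern holds for the selection rule. Section 11.4.3 asks attrition monitoring to settle a question that it cannot settle, and uses the answer to choose the analysis that checks the completer result. At 30% missing, each point of difference between leavers and completers moves the whole-cohort change by 0.3, and about 8.3 points removes or doubles a 2.5-point completer change. In the simulation both estimates moved by roughly 0.9 to 2.9 points with no signal from the attrition test.

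The 0.3 factor rests only on the planned 30% attrition. The simulation also assumes the strength of dependence on unseen COST, groups unrelated to COST, and imputation from baseline alone. Groups that differed in burden could show unequal attrition, but that would still not separate the two mechanisms. Using 3- and 6-month COST should reduce bias as far as those scores predict the 12-month one.

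On death the supportable statement is narrow: read literally, 11.4.1 and 11.4.3 do not exclude deceased patients from imputation. The documents give no death rate for this population, so no size is attached.

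**What to change.** In Section 11.4.3, delete the step that determines whether dropout is informative. Whatever the attrition pattern, always run both:

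- (a) a missing-at-random analysis of the 12-month change, using baseline, 3- and 6-month COST and recorded covariates;
- (b) a delta-adjusted analysis that shifts imputed 12-month COST over a fixed grid in both directions, for example -10 to +10 points in steps of 2.5, and reports the delta, if any, at which the conclusion changes. At 30% missing this grid moves the cohort mean by -3.0 to +3.0 in steps of 0.75, so it spans the 8.3-point difference.

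The monitoring in 11.3.3 can stay for its stated purpose of managing recruitment and oversampling.

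As a secondary clarification, state in 11.4.1 and 11.4.3 how deaths are handled. One option is to define the 12-month change among patients alive at that time and report deaths separately from the vital status already collected. Other definitions are legitimate if stated in advance.

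The cost is SAP wording and one more scripted analysis, with no change to sample size or data collection.
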